9.1 Definitions

- *PSA response rate*: The proportion of study patients with PSA <0.1 ng/mL at 21 months after completion of study treatment.
- *Acute toxicity*: Toxicity occurring during treatment and within three months of completing treatment.
- *Late toxicity*: Toxicity occurring more than three months after treatment completion. *Failure rate*: The cumulative incidence of biochemical or clinical failure allowing for competing risk as needed. Clinical failure is defined as at least a 25% increase in the size of the tumor relative to the smallest volume recorded, or new extension of tumor beyond the capsule, or re-extension of tumor beyond the capsule after initial regression, or urinary obstructive symptoms with carcinoma found at TURP. Biochemical failure is defined as PSA \geq nadir + 2 ng/mL.

- *Failure-free Survival (FFS)*: The elapsed time from start of radiotherapy to first documented evidence of biochemical or clinical failure or death from any cause, whichever occurs first. In the absence of any event defining failure, follow-up time will be censored at the date of last documented failure-free status.
- *Overall Survival (OS)*: The elapsed time from start of radiotherapy to death from any cause. For surviving patients, follow-up will be censored at the date of last contact.
- *Biomarker expression*: Quantification of the amount of the biomarker specific immunohistochemical staining in the area of tumor.
- *QOL*: Two contemporary instruments will be utilized to assess patient function and bother (Expanded Prostate Cancer Index Composite-SF12 (EPIC-SF12) and prostate cancer-specific anxiety Memorial Anxiety Scale for Prostate Cancer patients (MAX-PC).

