9.2 Guidelines for Evaluation of Measurable Disease

9.2.1 Clinical primary tumor response will be measured by palpation and recorded in the following ways:

- Pretreatment: A representative drawing of the pretreatment tumor status on DRE, if palpable, will be recorded in the radiotherapy chart.
- Post-treatment: The change in palpable tumor volume will be recorded qualitatively.

9.2.2 PSA levels:

In 98% of patients treated with salvage radiotherapy there is a drop in PSA within 3 months. Those patients that PSA levels have not dropped should be investigated to define the site of progression (local-regional vs. distant metastases). In the rest of the patients, a rising PSA later heralds relapse. Biochemical failure will be modeled after the Nadir+2 definition.[49] Evaluation of patients with a rising PSA profile will include a bone scan, MRI-pelvis/prostate bed, and prostate bed biopsy.

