Evaluable: Patients who are study eligible and receive an initial dose of *MTSRT* will be considered *evaluable for safety*, regardless of whether or not the full course of radiation treatment is completed according to protocol. To be *evaluable for efficacy*, study eligible patients must either (1) complete radiation treatment and the nine month post treatment PSA assessment or (2) initiate therapy but develop evidence of biochemical or clinical failure, or die from causes related to prostate cancer, within nine months of stopping or completing treatment. In the latter case (2), which is expected to be rare, patients will be included as non-responders in the evaluation of PSA response rate. The set of patients who are evaluable for efficacy comprise the main analysis set.

Exclusions: Any patient who is enrolled on study but does not receive an initial dose of radiation treatment will be excluded from all efficacy analyses. Any patient who initiates treatment and is later found to be ineligible for study (e.g., protocol violation) will be withdrawn from study but will be followed for toxicity and clinical outcome; the experience of such patients will be characterized separately from that of patients who are evaluable for efficacy. Reasons for exclusion of enrolled patients from analysis of safety or efficacy will be characterized.

Study endpoints are defined in **Section 9.1**.

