The primary trial endpoint, *PSA response rate*, will be estimated as a proportion with corresponding 95% confidence interval by the exact binomial method. Biomarker and proteomic/genomic characteristics of baseline prostate bed biopsy tissue will be summarized by descriptive statistics. Additionally, biomarker and proteomic/genomic characteristics measured in blood samples obtained at baseline, RT completion, and 3 months post RT will also be studied and changes from baseline will be tested for significance using t-test (means) or McNemar's test (proportions) for paired data. (For biomarker studies, nonparametric tests or data transformations to attain approximate normal distributions will be applied as needed.) Logistic regression models will be used to investigate the association between baseline factors, including biomarkers and proteomic/genomic profiles, and PSA response. Changes in biomarkers and proteomic/genomic characteristics measured in blood will also be investigated for association with PSA response.[52]

Patients will be followed for disease progression and vital status for a period of five years after completing study treatment. Progression of disease will be categorized as biochemical failure (BF), clinical failure (CF), or combined (BF + CF), where combined failure refers to documented evidence of BF and CF occurring within 6 months of each other with the earlier date used. CFs will be further categorized as local, nodal, or distant. Start of subsequent therapy will be considered a failure event for selected analyses as indicated in the table below. Deaths will be categorized as related/unrelated to prostate cancer. The number of observed failures will be tabulated by failure type. Similarly, vital status will be tabulated by presence or absence of disease at last follow-up.

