Time to event endpoints will be analyzed by Kaplan-Meier (KM) or competing risk (CR) methods as indicated in Table 14.5.[53, 54] Where the Kaplan Meier method is used, point estimates and 2-sided 95% confidence intervals for event-free rates will be reported for selected times such as 1, 2 and 5 years from treatment start using Greenwood's variance and the log-log transform method. Median event-free or overall survival time, if attained, will also be reported. Cox regression models will be used to explore the prognostic effect of baseline characteristics as well as biomarkers and proteomic and genomic profiles. Regression findings will be expressed as hazard ratios and corresponding 95% confidence intervals. For analyses involving competing risks, cumulative incidence rates will be reported for selected times with corresponding 2-sided 95% confidence intervals based on the variance estimator of Aalen and the log-log transform method. Regression models investigating prognostic factors will be fit by the method of Fine and Gray. [55, 56] Where study data indicate that at most a small number of competing risk events have occurred, analysis will be simplified by treating such events as censored observations in a Kaplan-Meier analysis, since the resulting overestimation of the event rate will be negligible.

Table 14.5. Time-to-event endpoints.

Endpoint	Analysis	Events (earliest)	Competing risks	Censoring
Failure rate	CR	CF, BF, BF+ CF (within 6 months of each other). Start subsequent therapy. Death related to prca without prior evidence of failure.	Death unrelated to prca	Last clinical +PSA assessment
Toxicity rate (to be done separately for GI and GU)	CR	Onset of grade 2+ and 3+ toxicity	Start subsequent therapy Death, any cause	Last contact
Failure free survival (FFS)	KM	CF, BF, BF+ CF. Start subsequent therapy. Death, any cause.	n/a	Last clinical or PSA assessment
Prostate cancer mortality	CR	Death related to prca	Death unrelated to prca	Last contact
Overall survival (OS)	KM	Death, any cause	n/a	Last contact

KM: Kaplan-Meier. **CR:** competing risk. **BF:** Biochemical failure. **CF:** clinical failure. **prca:** prostate cancer. **GI:** gastrointestinal. **GU:** genitourinary.

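### The primary PSA endpoint has no rule for therapy started before the endpoint PSA, so a man re-treated to below 0.1 ng/mL counts as a responder to the boost

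*Combined protocol and SAP*

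**What the plan says.** **Endpoint.** Section 9.1 defines PSA response rate as "The proportion of study patients with PSA <0.1 ng/mL at 21 months after completion of study treatment". Sections 9.0, 14.1 and 14.2 give the same 21-month time point. None of them sets a condition on treatment given between the end of radiotherapy and that PSA.

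**Evaluability and forced non-response.** Section 14.3 makes an eligible man evaluable for efficacy by one of two routes. Either he must "complete radiation treatment and the nine month post treatment PSA assessment", or he must start therapy but "develop evidence of biochemical or clinical failure, or die from causes related to prostate cancer, within nine months of stopping or completing treatment". Only the second route makes a man a non-responder whatever his PSA. It does not list start of subsequent therapy, and it closes at nine months.

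**Subsequent therapy elsewhere.** Section 14.5 says "Start of subsequent therapy will be considered a failure event for selected analyses as indicated in the table below". For FFS the table's events are "CF, BF, BF+ CF. Start subsequent therapy. Death, any cause". The table also makes subsequent therapy an event for the failure rate and a competing risk for toxicity. PSA response is not in the table.

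**FFS in 9.1.** Section 14.3 refers to 9.1 for endpoint definitions, and there FFS is "The elapsed time from start of radiotherapy to first documented evidence of biochemical or clinical failure or death from any cause". Subsequent therapy is absent, so 9.1 and Table 14.5 disagree on FFS.

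**Planned therapy.** The note in 3.2 allows androgen deprivation given as part of the planned radiation course.

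**The concern.** The trial asks whether the boost produces an undetectable PSA. A PSA that is low because another treatment was started does not answer that. The plan accepts this for the failure rate and for FFS in Table 14.5, but gives no matching rule for the primary endpoint.

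A man can need further treatment without meeting a failure definition. Biochemical failure requires nadir + 2 ng/mL, whereas response requires a PSA below 0.1, and a man between those levels is neither. There are points before month 21 at which his management could change: imaging at 3 and 9 months (Section 5.4; the 9-month MRI is at the PI's discretion in Appendix I), and the work-up of a PSA that has not fallen or is rising (Section 9.2.2).

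The design is one arm against a fixed 60%, so no concurrent control shares the scoring rule. Section 14.1 says the result will inform a later trial.

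**Working it through.** **1. The plan's own figure.** Inputs from 14.2: n = 40, null rate 60%, alternative 80%, one-sided 5%. The test is called Fisher's exact, but with one arm it is a one-sample exact binomial. The smallest r with P(X ≥ r | 0.60) ≤ 0.05 is r = 30:

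- P(X ≥ 29 | 40, 0.60) = 0.0709
- P(X ≥ 30 | 40, 0.60) = 0.0352
- P(X ≥ 30 | 40, 0.80) = 0.8392, which reproduces the stated 83.9%

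The stated power is correct on its own terms.

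**2. Cases traced through the text.** In each, the man completes radiotherapy and has his nine-month PSA.

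| Course | FFS, Table 14.5 | PSA response, 9.1 and 14.3 |
|---|---|---|
| Documented failure by month 9, then re-treated | Failure | Non-responder |
| Re-treated without documented failure, below 0.1 at month 21 | Failure | Responder |
| Documented failure between months 9 and 21, re-treated, below 0.1 at month 21 | Failure | Responder |
| Biochemical failure (nadir + 2), not re-treated, PSA stays up | Failure | Non-responder on PSA itself |

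The third row arises because the failure window stops at nine months while the endpoint is at 21. If the endpoint were at nine months, as the timing text in 8.0, 14.2 and 14.5 still has it, that row would disappear. The gap would then be limited to men re-treated before month nine without documented failure.

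**3. Illustrative size.** The documents give no re-treatment rate. Let s be the assumed share of true non-responders who are re-treated to below 0.1 and counted as responders. With a true rate of 60%, the apparent rate is p = 0.60 + 0.40s, and the expected number of masked men is 40 × 0.40 × s.

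| s | Masked men of 40 | Apparent rate | P(X ≥ 30), one-sided rule in 14.2 | P(X ≥ 31), two-sided rule in 14.5 |
|---|---|---|---|---|
| 0% | 0 | 60% | 3.5% | 1.6% |
| 2.5% | 0.4 | 61% | 4.6% | 2.1% |
| 5% | 0.8 | 62% | 6.0% | 2.9% |
| 10% | 1.6 | 64% | 9.7% | 5.0% |

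**4. Dependence on the benchmark.** The table assumes that the source of the 60% counted re-treated men as non-responders. If it counted them as responders in the same proportion, the error stays at 3.5% for every s. If half were matched, the 10% row becomes p = 0.62 and the error 6.0%.

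**5. The only related figure in the documents.** Section 9.2.2 states "In 98% of patients treated with salvage radiotherapy there is a drop in PSA within 3 months". The remaining 2% is 0.02 × 40 = 0.8 men, or 0.8 / 16 = 5% of the 16 non-responders expected at a true 60%. So s = 5% is a ceiling for that early route alone. It would require every such man to be re-treated, to have no documented failure by month nine, and to reach below 0.1.

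**6. Near the boundary.** One masked man moves 29/40 (one-sided p = 0.071) to 30/40 (p = 0.035). Under the exact 95% interval in 14.5, one man moves 30/40 (58.8% to 87.3%, includes 60%) to 31/40 (61.5% to 89.2%, excludes 60%).

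**The case against.** **The existing rule catches part of this.** Section 9.2.2 says "Those patients that PSA levels have not dropped should be investigated to define the site of progression". If a site is found within nine months, the man has evidence of clinical failure and is already a non-responder. The same section does not say that such men are treated, and 5.4 says only that management is discussed if a lesion is seen. This stands. A reader might infer from the 98% figure that 2% of men are re-treated and masked, but the documents do not support that.

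**Much of the reach comes from the nine-month window.** This also stands, but a gap remains once the window is fixed, because subsequent therapy is not listed at either time point.

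**PSA status regardless of later therapy is a legitimate endpoint, and 14.5 limits the failure rule to selected analyses.** It is a recognised choice, but the plan neither states nor justifies it. It also fits poorly with an objective about the effect of the boost. It belongs in the plan as a sensitivity analysis.

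**The error rates are assumptions.** They are. A reader might take 6.0% or 9.7% as this trial's false-positive rate. The 10% row has no basis in the documents, zero is possible, and the figures do not apply if the benchmark was scored alike. That one man can tip the result near a boundary is true of any threshold and is not evidence of bias.

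**A broader reading.** A reader might also count as an error that a man with clinical failure after month nine, no re-treatment and a PSA below 0.1 is a responder. Whether a PSA endpoint should become a composite is debatable, and it is not part of this point.

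**Conclusion.** The point holds as a gap in the primary endpoint's scoring rule and should be fixed. Followed exactly, the plan counts as a responder a man who starts unplanned prostate cancer therapy before the endpoint PSA and is then below 0.1. That includes a man with documented failure between months 9 and 21 who is then re-treated.

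The direction is certain only relative to response without re-treatment: the observed rate can rise but not fall. Bias against the 60% is not established, because the documents do not say how its source scored re-treated men. The size is unknown and may be zero, and the error rates above show sensitivity only. The sample-size calculation is not shown to be wrong: 40 men, the boundary of 30 and the power of 83.9% all stand if 60% and 80% mean response without re-treatment. Confidence is medium.

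**What to change.** 1. In 9.1 and 14.3, score as a non-responder any man who, before the primary-endpoint PSA, starts prostate cancer therapy that was not recorded at enrolment as part of the planned radiation course. The 3.2 note supplies the distinction, so planned androgen deprivation is not penalised.
2. Run the forced non-response window in 14.3 up to the primary-endpoint PSA, and reconcile evaluability with that time point. This also carries the plan's existing scoring of clinical failure beyond month nine, so the text should say whether that is intended for men who are not re-treated.
3. Report PSA response regardless of subsequent therapy as a sensitivity analysis, and state how the source of the 60% scored re-treated men.
4. Align the FFS definition in 9.1 with Table 14.5.

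**Cost.** Wording, one enrolment field for the planned course, and one extra table. The start of subsequent therapy is already needed for Table 14.5. The change affects scoring, not treatment. The reported rate may be slightly lower. If 60% and 80% are in fact rates regardless of therapy, and re-scoring lowered the 80% to 79% or 78% (assumed), power would fall from 83.9% to P(X ≥ 30 | 40, 0.79) = 79.6% or P(X ≥ 30 | 40, 0.78) = 74.8%. That is why the benchmark's rule should be stated together with the new scoring.

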4.6 Prostate Bed Conformal PTV Planning and Constraints

Patients will be randomized to one of two study arms as described in Section 3.3. Image-guided technique will be used to deliver the fractionation treatments to minimize the dosimetric error. The Clinical Target Volume (CTV), will include the Prostate/SV bed (with MRI GTV). The Planning Target Volume (PTV) will

be 7 mm around the CTV in all dimensions. All patients will be treated with IMRT. The isodose level of the prescription dose shall be kept to 85% or higher, covering the clinical target volume (CTV: prostate bed) plus a planning target volume (PTV) for uncertainty of 7 mm everywhere, except posteriorly, where the margin would be an average 7 mm (6 – 8 mm is acceptable). The pelvic lymph may be treated to a dose of 51-54 Gy at the treating physicians discretion as long as dose constraints for normal tissues are met. The prescription dose to at least 95% of the PTV is 68 Gy using IMRT in 34 fractions, the mapped tumor (MT) boost region will receive an absolute dose of 76.5 Gy in 34 fractions. Assuming an α/β ratio of 3.0, this would be equivalent to 80 Gy in 2.0 Gy fractions.

Treatments usually are given 5 times per week. The bladder, rectum, penile bulb and urethra will be defined on the CT and MRI scans. Dose volume histogram (DVH) analysis will be used to assess plan acceptance per the RTOG guidelines. These include:

Rectum: Less than or equal to 35% and 55% of the rectum should receive \geq 65 Gy and \geq 40 Gy, respectively. A variation will be noted if up to an additional 10% of the rectal volume receives above the target doses specified. The inclusion of rectal volumes beyond these constraints will be considered a protocol violation. In many patients, these constraints may be easily met and every attempt should be made to achieve the best dose distribution possible.

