Bladder: Less than or equal to 50% and 70% of the bladder (minus prostate bed CTV) should receive \geq 65 Gy and \geq 40 Gy, respectively. The criteria for the bladder have been relaxed because the dosimetric relationship of volume exposed to the specified marker doses is much less clear and the bladder neck is included in the CTV. A primary variation will be noted if up to an additional 7.5% of the bladder volume receives above the target doses specified. The inclusion of bladder volumes beyond these constraints will be considered a secondary protocol variation; it will not be considered a protocol violation. In some patients, the bladder will be relatively empty and the majority will be in the PTV.

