13.0 DATA REPORTING

Data must be submitted according to the protocol requirements for ALL patients registered. Patients for whom documentation is inadequate to determine eligibility will generally be deemed ineligible.

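### Sections 14.3 and 13.0 let a treated man be ruled ineligible after treatment, on grounds not confined to the entry criteria and with no requirement to decide before the endpoint PSA is known; near the boundary one such exclusion can change the primary conclusion.

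*Combined protocol and SAP*

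**What the plan says.** Section 14.3 admits only study-eligible patients to both evaluable sets, safety and efficacy, and adds: "The set of patients who are evaluable for efficacy comprise the main analysis set". On treated men it says: "Any patient who initiates treatment and is later found to be ineligible for study (e.g., protocol violation) will be withdrawn from study". They are still followed for toxicity and clinical outcome, but "the experience of such patients will be characterized separately from that of patients who are evaluable for efficacy". There is one transparency provision: "Reasons for exclusion of enrolled patients from analysis of safety or efficacy will be characterized".

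Section 13.0 supplies a second route to ineligibility: "Patients for whom documentation is inadequate to determine eligibility will generally be deemed ineligible". Section 3.3.1 already requires a completed and signed eligibility checklist before enrollment.

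Section 14.3 does not define protocol violation. Section 4.6 uses the same term for dose-volume results. For the rectum there is first a tolerance band: "A variation will be noted if up to an additional 10% of the rectal volume receives above the target doses specified". Beyond that, "The inclusion of rectal volumes beyond these constraints will be considered a protocol violation". For bladder volumes beyond their own band, 4.6 says the opposite: "it will not be considered a protocol violation".

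Section 14 gives no date by which ineligibility must be decided, names nobody to decide it and does not require that person to be unaware of the PSA result. Section 14.7, whose title covers exclusions, is marked not applicable. Section 4.11 mentions an intent-to-treat analysis, but section 14 defines none.

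**The concern.** An entry criterion is a fact about a man before treatment. A protocol violation is ordinarily something that happens during the conduct of the trial. By giving the second as its only example of the first, 14.3 blurs the line between a man who should not have been enrolled and a man whose treatment departed from plan. The word "generally" in 13.0 leaves further discretion.

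The trial is open and single-arm, and the primary result is one proportion set against a fixed 60%. No comparator arm would undergo the same exclusions, so every change in the denominator moves the result directly. With no cut-off, a ruling can be made when the man's PSA is already known. Because the safety set also requires eligibility, a man ruled ineligible may drop out of the toxicity rates too. The text does not say whether he still counts in Table 14.6.1.

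**Working it through.** **Inputs.** Null rate 60%, alternative 80%, 40 evaluable men, one-sided 5% exact test, stated power 83.9% (14.2). Two-sided 5% tests and an exact 95% confidence interval (14.5). Late-toxicity prior Beta(0.2, 1.8), limit 10%, guideline at 80% posterior probability (14.6).

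**The plan's own figure.** Section 14.2 names Fisher's exact test. With one arm and a fixed 60%, the calculation that matches is the one-sample exact binomial. The smallest r with P(X ≥ r | 40, 0.60) ≤ 0.05 is r = 30:
- P(X ≥ 30 | 40, 0.60) = 0.0352
- P(X ≥ 30 | 40, 0.80) = 0.8392, which agrees with 83.9%.

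**Removing non-responders, one-sided test of 14.2.** Formula: p = P(X ≥ x | n, 0.60).

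| Result | p | At 5% |
|---|---|---|
| 29/40 | 0.0709 | fails |
| 29/39 (one removed) | 0.0450 | passes |
| 29/38 (two removed) | 0.0268 | passes |

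**Two-sided reading of 14.5.** Success means that the exact 95% lower limit exceeds 0.60.

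| Result | Lower limit | Two-sided p | Verdict |
|---|---|---|---|
| 29/39 | 0.579 | 0.073 | fails |
| 30/40 | 0.588 | 0.054 | fails |
| 30/39 | 0.607 | 0.033 | passes |

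One removal changes the conclusion on either reading, but from a different starting count.

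**The opposite direction.** Start from 30/40 on the one-sided test (p = 0.0352, passes). Removing one responder leaves 29/39 (0.0450, passes); removing two leaves 28/38 (0.0572, fails). Exclusions can also turn a success into a failure.

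**How often the boundary matters.** Exactly 29/40 has probability 3.6% at a true rate of 60%, 13.2% at 70% and 7.3% at 80%. On the one-sided test the one-man change also occurs at 37, 38, 41, 43 and 44 evaluable men. It does not occur at 36, 39 or 42, where two removals are needed.

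**Upper bound on type I error.** Suppose that non-responders were removed whenever that helped. With one removal allowed, the rule at 40 becomes 29 or more, and the one-sided error rises from 0.0352 to 0.0709. It stays at 0.0709 with up to two removals and reaches 0.1285 with up to three. These are worst cases, not expected rates.

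**Safety set.** The posterior for late toxicity with x events in n men is Beta(0.2 + x, 1.8 + n − x). For 2/8, P(rate > 10%) = 82.6%, as in the illustration in 14.6, so the guideline is met. If one of the two men with an event were left out, 1/7 gives Beta(1.2, 7.8) and 52.5%, and it is not met.

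**The case against.** The strongest reply is that the operative words in 14.3 concern ineligibility and the parenthesis only illustrates it. A reader might infer that a rectal dose-volume breach under 4.6 makes a man ineligible. No section says so. The link is one shared, undefined term, and the 4.6 violation begins only beyond the additional 10% band. Section 14.3 also keeps eligible men evaluable for safety whether or not treatment was completed per protocol, and for efficacy it asks for completed treatment rather than treatment within dose limits. This stands: the text permits exclusion for a delivery deviation but does not state it.

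A reader might also infer that such exclusions favour the boost, or that a rectal breach shows the boost could not be planned within limits. Neither is supported. Nothing in the documents ties rectal dose or missing papers to PSA non-response, and the Schema gives the same rectal limits for the closed standard arm, which had no boost.

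Section 13.0 concerns documents needed to determine eligibility, not poor record-keeping at large, and the signed checklist should make such cases uncommon. That also stands.

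Finally, withdrawn men are followed and the reasons for exclusion are reported, so an attentive reader could partly rebuild an all-treated result. This helps, but the primary denominator would still rest on rulings that may post-date the outcome. Any exact test changes at its boundary; the objection here is that the plan leaves open who is counted there.

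**Conclusion.** The concern holds as a gap in the definition of the analysis sets. Ineligibility after treatment is not limited to entry criteria, need not be decided before the endpoint PSA is known, and is not backed by an analysis of all treated men. At the planned 40 men, one exclusion can change the primary conclusion: 29/40 to 29/39 on the one-sided test, or 30/40 to 30/39 on the two-sided interval. It would be too strong to say that 29/39 is a success on any reading, since it fails under 14.5.

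The size rests on three assumptions: the exact binomial test against 60%, a result on the boundary, and removal of a non-responder. The documents do not show that exclusions would run in that direction, how many there would be, or that anyone would choose them knowing the PSA. The toxicity example likewise assumes that a man ruled ineligible is left out of the monitoring count, a point on which the text is silent. The change is worth making because it is cheap and removes a discretion that the primary result does not need.

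**What to change.** - **14.3:** delete the protocol-violation example. Define ineligible as failing a criterion in 3.1 or 3.2 on facts dated before the first fraction, decided and recorded without knowledge of the endpoint PSA.
- **13.0:** state that a treated man with a signed pre-enrollment checklist stays in the analysis sets if documents later prove incomplete.
- **14.3 and 14.5:** keep men with treatment-delivery deviations in the response and toxicity analyses, including the counts used in Table 14.6.1, and tabulate the deviations.
- **14.5:** add a sensitivity analysis of PSA response in every man who received a first dose, with excluded or unassessed men counted as non-responders. For scale, a fixed denominator of 44 would need 33 responders (one-sided level 0.0277; power 84.6% if the true rate across all 44 is 80%). Counting unassessed men as failures would lower that rate, so this belongs beside the main analysis.

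The cost is protocol and SAP wording, with no new patients, visits or data. A few men later found ineligible or poorly documented may remain in an analysis, and the response or toxicity figures may shift slightly in either direction.
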